#### 3.2 Analysis of Categorical Data

C/F noted in the mock-up table, Chi-Square test is applied when no cell have expected count  $< 1$  and  $<= 20\%$  of the cells are with expected count  $< 5$ , otherwise Fisher's exact test will be applied.

## (2) Treatment Group:

CX-4945: The best supportive / standard of care + CX-4945 1000 mg BID ,  
 SOC : The best supportive / standard of care

## (3) Population

- ITT (Intention-To-Treat):  
 All randomized patients
- Safety Population:  
 Receiving at least one dose of CX-4945 or being randomized to the standard of care arm.
- PP (Per-Protocol):  
 A subset of ITT and Safety population who are not associated major protocol deviation relevant to efficacy analysis.

If Safety Population and ITT are the same, these two populations will be combined as 'Safety Population and Intention-To-Treat' if results of both populations are to be presented in the same table.

## (4) For Visit Name (in Tables and Figures) and Visit Code (in Subject Data Listing):

Visit No.	Visit Description	Visit Day	Visit Name	Visit Code
1	Screening Visit	-7 ~ -1	Visit 1 (Screening)	V01
2	Treatment Visit (Day 1)	1	Visit 2 (Day 1)	V02D01T
3	Treatment Visit (Day 4)	4 ± 1	Visit 3 (Day 4)	V03D04T
4	Treatment Visit (Day 8)	8 ± 1	Visit 4 (Day 8)	V04D08T
5	Treatment Visit (Day 11)	11 ± 1	Visit 5 (Day 11)	V05D11T
6	End of Treatment (EOT)Visit (Day 14)	14 ± 1	Visit 6 (Day 14, EOT)	V06D14E
7	Follow-up 1 Visit (Day 28)	28 ± 3	Visit 7 (Day 28, F1)	V07D28F
8	Follow-up 2 Visit (Day 45)	45 ± 3	Visit 8 (Day 45, F2)	V08D45F
9	Follow-up 3 Visit (Day 60)	60 ± 3	Visit 9 (Day 60, F3)	V09D60F
	Unscheduled Visit	-	-	UV

## (5) Efficacy Endpoints:

- **Time to COVID-19-Related Clinical Signs Normalization: Normal when all below are met**
  - (1) Fever is <36.6°C from axillary site, or < 37.2°C from oral site, or < 37.8°C from rectal or tympanic site, or <37.2°C from forehead by using non-contact infrared thermometers
  - (2) Respiratory rate is < 20 bpm while breathing room air
  - (3) SpO2 ≥ 96% in room air without shortness of breath or dyspnea caused by COVID-19
  - (4) Heart rate < 90 beats per minute

If some signs listed above were caused by other conditions documented in the medical history and started before COVID-19, the patient can be considered as recovered, when these signs return to the previous (pre-COVID-19) values
- **Oxygen Saturation Level Normalization: Normal when SpO2 ≥ 96%**
- **Resolution of moderate COVID-19-Related Symptoms when all below are met:**
  - No key COVID-19-related symptoms scored higher than 1.
  - If some symptoms were caused by other conditions documented in the medical history and started before COVID-19 (e.g, insomnia), the patient can be considered as recovered, when these symptoms return to the previous (pre-COVID-19) value.
- **SARS-CoV-2 Viral Clearance: negative RT-PCR**

- **NIAID 8-Point Clinical Progression Outcomes Scale:**
  - 1 - Death
  - 2 - Hospitalized, on invasive mechanical ventilation or extracorporeal membrane oxygenation (ECMO)
  - 3 - Hospitalized, on non-invasive ventilation or high flow oxygen devices
  - 4 - Hospitalized, requiring supplemental oxygen
  - 5 - Hospitalized, not requiring supplemental oxygen - requiring ongoing medical care (COVID-19 related or otherwise)
  - 6 - Hospitalized, not requiring supplemental oxygen - no longer requires ongoing medical care
  - 7 - Not hospitalized, limitation on activities and/or requiring home oxygen
  - 8 - Not hospitalized, no limitations on activities
- **EQ-5D-5L Imaginable Health Status Improvement: Imaginable Health Status <90 at baseline and ≥ 90 after baseline**
- **Time to Response (Normalization / Resolution / Viral Clearance / Improvement)**

Time to Response (days), Best Case Scenario  
 = Days to first response for responder,  
 = Days to last observation for non-responder (censored)

Time to Response (days), Worst Case Scenario  
 = Days to first response for responder,  
 = Days to planned last observation date (31 for EQ-5D-5L and SARS-COV-2 Viral Clearance at visit 7, 45 for others at visit 8) for non-responder (censored)

Days to first response = date of first response – the first treatment date/time + 1

Days to last observation = date of last evaluation – the first treatment date/time + 1

For Arm SOC, the first treatment date is the date of visit 2

- (6) For Clinical Relevance
 

CS: abnormal and clinically significant	LLN: lower limit of normal range
NCS: abnormal but not clinically significant	ULN: upper limit of normal range
- (7) For Transition of Clinical Relevance
 

Relieved	CS (Medical History or Adverse Event) at baseline to Normal / NCS at visit.
Unchanged	Including Normal at baseline to NCS at visit, NCS at baseline to Normal at visit.
Worsened (Medical History)	Normal / NCS at baseline to CS (Medical History) at visit
Worsened (Adverse Event)	Normal / NCS / CS (Medical History) at baseline to CS (Adverse Event) at visit

If both 'Medical History' and 'Adverse Event' are checked for 'CS', it will be counted as 'Adverse Event' only.

- (8) Abbreviations of Statistics
 

N: number of non-missing values	ANOVA: analysis of variance
M: missing, not available	ANCOVA: analysis of covariance
Missing: number of missing values	CHISQ: Chi-Square test
Mean: mean of values	FISHER: Fisher's exact test
SD: standard deviation of values	MHCHISQ: Mantel-Haenszel chi-square test on given scores
Q1: 25% quartile of values	T: two sample t test
Q3: 75% quartile of values	W: Wilcoxon rank-sum test
Median: median of values	Diff.: difference
IQR: inter-quartile-range (IQR=Q3-Q1)	
Min: minimum of values	
Max: maximum of values	
CI: confidence interval	
LS-mean: least-square mean	

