	To evaluate other Clinical Benefit of treatment with CX-4945 relative to the control arm	
• All-cause mortality status – the number of deaths occurred in each treatment group from Randomization (Day 1) through Day 60.• Number of respiratory failure (i.e., need for mechanical ventilation, ECMO, noninvasive ventilation, or high-flow nasal cannula oxygen delivery) occurred in each treatment group from Randomization (Day 1) through Day 45.• Number of patients hospitalized in each treatment arm from Randomization (Day 1) to Day 45• Number of days to normalization of oxygen saturation level measured by pulse oximeter at Randomization (Day 1), Day 4, Day 8, Day 11, Day 14, Day 28 and Day 45 and categorized as <96% versus ≥96%. Proportion of patients with disease progression or improvement in health status occurring from Randomization (Day 1) to Day 28. Disease progression is defined as change in patient health status assessment from item 7 to items 1- 6 and health improvement -as change from item 7 to item 8, evaluated by the ordinal NIAID 8-Point Clinical Progression Outcomes scale collected at every visit from Day 1 through Day 45. 
The 8-category ordinal scale of patient health status ranges from:
 
1. Death;2. Hospitalized, on invasive mechanical ventilation or extracorporeal membrane oxygenation (ECMO);

		
3. Hospitalized, on non-invasive ventilation or high flow oxygen devices;4. Hospitalized, requiring supplemental oxygen;5. Hospitalized, not requiring supplemental oxygen - requiring ongoing medical care (COVID-19 related or otherwise);6. Hospitalized, not requiring supplemental oxygen - no longer requires ongoing medical care;7. Not hospitalized, limitation on activities and/or requiring home oxygen;8. Not hospitalized, no limitations on activities. 
• Changes in EQ-D5-5L (used as an indicator of symptom improvement) from randomization (Day 1) to Day 8, Day 14 and Day 28.
	To evaluate changes in inflammatory markers	
• Changes in plasma IL-6 level from randomization (Day 1) to Day 4, 8, 11, and 14.• Changes in CRP, LDH, CPK, ferritin, D-dimer from randomization (Day 1) to Day 4, 8, 11, and 14.

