8.2.1.3. Vital Signs and Physical Examination

Patients will have a full physical examination to include an examination of all major body systems, height (at screening only), weight, blood pressure and pulse rate, which may be performed by a physician, registered nurse or other qualified health care provider, as acceptable according to local regulation. Symptom-directed physical examination should be limited to systems of primary relevance (i.e., cardiovascular, respiratory, and systems associated with symptoms). Changes from baseline abnormalities should be recorded at each subsequent physical examination. New or worsened abnormalities should be recorded as an AE.

Pulse oximetry should be collected prior to collection of the blood pressure, pulse rate, and temperature. Oxygen levels should be evaluated on the finger in accordance with the site's standard procedures. All abnormalities will be evaluated by the study physician.

Blood pressure, heart rate, respiration rate, and temperature should be recorded after approximately 5 minutes rest. An abbreviated physical exam is an assessment for emergent toxicities or changes from prior visits and a symptom directed exam conducted by a physician, trained physician's assistant or nurse practitioner, as acceptable according to local regulation.

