### 14.3.8 Vital Signs, Body Weight and SpO2

- 14.3.8.1 Vital Signs – Temperature [degree C]
- 14.3.8.2 Vital Signs – Respiratory Rate [breaths/min]
- 14.3.8.3 Vital Signs – Systolic Blood Pressure [mmHg]
- 14.3.8.4 Vital Signs – Diastolic Blood Pressure [mmHg]
- 14.3.8.5 Vital Signs – Heart Rate [beats/min]
- 14.3.8.6 Vital Signs – Weight [kg]
- 14.3.8.7 Vital Signs – Pulse Oxygen Saturation (SpO2) [%]

Population: Safety Population		Treatment Group	p-value
Characteristics			
. Repeat Visit:			
Visit 1 (Screening), Baseline,			
Adjusted Visit 3 (Day 4), Adjusted Visit 4 (Day 8), Adjusted Visit 5 (Day 11),			
Adjusted Visit 6 (Day 14, EOT), Visit 7 (Day 28, F1), Visit 8 (Day 45, F2)			
N (Missing)	XXX (XXX)		
Mean (SD)	XXX (XXX)		
Median (IQR)	XXX (XXX)		
Q1~Q3	XXX~XXX		
Min~Max	XXX~XXX		
For W, normality is not applied		§C - §S	
Groups Diff			
Median (Asymptotic SE)	XXX		
95% CI (HL)	XXX~XXX		
For T, normality is applied		§C - §S	
Groups Diff			
Mean (SD)	XXX (XXX)		
95% CI	XXX~XXX		
For Temperature, Respiratory Rate, Heart Rate, Pulse Oxygen Saturation (SpO2)			
Normal	XXX (XXX.X%)	C/F	
Abnormal	XXX (XXX.X%)	0.XXXX	
. Repeat [Visit – Baseline] excluding Visit 1 (Screening) and Baseline			ANCOVA/W
N (Missing)	XXX (XXX)		0.XXXX
Mean (SD)	XXX (XXX)		
Median (IQR)	XXX (XXX)		
Q1~Q3	XXX~XXX		
Min~Max	XXX~XXX		
95% CI (WI)	XXX~XXXwt		
For W, normality is not applied		§C - §S	
Groups Diff			
95% CI (HL)	XXX~XXX		
For ANCOVA, normality is applied		XXX (XXX)	
		XXX~XXX	
LsMean (SE)			
95% CI of LsMean			
Groups Diff. (T)	§C- §S		
Difference of LsMean	XXX		
95% CI of LsMean	XXX~XXX		

ANCOVA Model (p-value 0.XXXX) with effect Treatment (p-value 0.XXXX), Baseline (p-value 0.XXXX), Treatment\*Baseline (p-value 0.XXXX).

Baseline is Visit 2 (Day 1) data, or is Visit 1 if Visit 2 (Day 1) is null

[Temperature] Normal: <36.6°C from axillary site, or < 37.2°C from oral site or < 37.8°C from rectal or tympanic site

[Respiratory Rate] Normal: < 20 breaths/min

[Heart Rate] Normal: <90 beats/min

[Pulse Oxygen Saturation (SpO2)] Normal: ≥ 96%

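### The separate oxygen-saturation endpoint does not require room air, so a patient who worsens and then reads 96% or more on oxygen can be scored as normalized on it

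*SAP*

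**What the plan says.** Protocol 1.1 and 3 list, among the other clinical-benefit endpoints, "Number of days to normalization of oxygen saturation level measured by pulse oximeter" on Days 1, 4, 8, 11, 14, 28 and 45, "categorized as <96% versus ≥96" per cent. The SAP (Instructions, item 5) carries this over as "Oxygen Saturation Level Normalization: Normal when SpO2 ≥ 96" per cent. The footnote to table 14.3.8.7, which governs the by-visit Normal/Abnormal row, reads "Pulse Oxygen Saturation (SpO2)] Normal: ≥ 96" per cent. None of these mentions room air.

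The same SAP list words the SpO2 item of the clinical-signs endpoint differently: "SpO2 ≥ 96% in room air without shortness of breath or dyspnea caused by COVID-19". Protocol 1.1, 3 and 8.2.2.2 also require room air for that endpoint.

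SAP 1.4.2 analyses time to oxygen-saturation normalization by Kaplan-Meier and log-rank. A responder's time is the day of first response in both scenarios. The scenarios differ only in where a non-responder is censored: at the last observation (best case) or at the planned last day, 45 for this endpoint (worst case). Results are to be called robust if the two agree.

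**The concern.** SpO2 measured on supplemental oxygen reflects the support as well as the patient. If such a reading can meet the definition of normal, needing oxygen can itself produce the favourable event.

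The plan foresees oxygen use. Item 4 of the 8-point scale is "Hospitalized, requiring supplemental oxygen", items 2–3 cover ventilation and high-flow oxygen, and item 7 is "Not hospitalized, limitation on activities and/or requiring home oxygen". SAP table 14.1.8 has a row for supplemental oxygen. The trial is open label and supportive care is at the investigator's discretion, so oxygen use may differ between arms. If it does, the arm with more deterioration could show the faster normalization curve, with a log-rank p-value attached. The bias favours whichever arm uses more oxygen; the documents do not say which that would be.

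**Working it through.** The plan gives no figure to reproduce: about 20 patients are chosen by clinical judgment, with no power, effect size or alpha. The check is therefore a comparison of texts followed by an illustration on invented data.

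**1. Definitions side by side.**

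| Place | SpO2 rule | Room air required? |
|---|---|---|
| Protocol 1.1 and 3, oxygen-saturation endpoint | ≥ 96% | No |
| SAP Instructions (5), oxygen-saturation endpoint | ≥ 96% | No |
| SAP 14.3.8.7, Normal/Abnormal row | ≥ 96% | No |
| Protocol 1.1, 3 and 8.2.2.2, clinical signs | ≥ 96% | Yes |
| SAP Instructions (5), clinical signs item 3 | ≥ 96% | Yes |

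**2. Does the measurement procedure supply the condition?** No. Protocol 8.2.1.3 says "Oxygen levels should be evaluated on the finger in accordance with the" site's standard procedures, and 8.2.2.5 refers to the schedule. Neither fixes or records oxygen status at the reading.

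**3. Who can be affected?** Exclusion criterion 1 removes patients with SpO2 of 93% or less on room air, and there is no upper limit. Day 1 is an assessment day and the SAP excludes nobody already at 96%, so such patients respond on Day 1 and a later fall does not change their time. The time-to-event endpoint is therefore exposed through patients still below 96%, in practice those entering at 94–95%. The by-visit row in 14.3.8.7 has no first-response rule, so there a reading on oxygen can count as normal at whichever visit it occurs.

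**4. Does the sensitivity analysis catch it?** Suppose a patient at 94% on Day 1 starts oxygen on Day 6 and reads 97% on Day 8. Best case: event on Day 8. Worst case: event on Day 8. The scenarios treat only non-responders differently, and this patient is a responder in both.

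**5. Illustration (all data assumed).** Ten patients per arm, all starting at 94–95%. Arm A normalizes on Days 4, 4, 8, 8, 8, 11, 11, 14, 14, 28; the median is (8 + 11)/2 = 9.5. Arm B is identical, except that its last k patients worsen, are on oxygen by Day 8 and read 96% or more on it. As written, they are events on Day 8. With room air required, they are censored at Day 45.

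| k | As written: B responders, median, log-rank p | Room air: B responders, median, log-rank p |
|---|---|---|
| 1 | 10/10, 8 days, 0.50 | 9/10, 9.5 days, 0.78 |
| 2 | 10/10, 8 days, 0.28 | 8/10, 9.5 days, 0.51 |
| 3 | 10/10, 8 days, 0.12 | 7/10, 9.5 days, 0.32 |
| 4 | 10/10, 8 days, 0.08 | 6/10, 9.5 days, 0.16 |

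As written, the arm that deteriorates looks faster. With room air required, it has fewer responders and the same median as Arm A.

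**6. A milder assumption.** Let only 2, 3 or 4 patients per arm start below 96%, with normalization days 8, 14; or 8, 11, 14; or 4, 8, 14, 28. Everyone else responds on Day 1, and the last 1 or 2 Arm B patients go on oxygen as above. The p-values run from 0.42 to 0.63 as written and from 0.31 to 0.76 with room air required. Both medians stay at Day 1. The direction of the error is the same, but its effect is small.

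**The case against.** The best defence is that deterioration is visible elsewhere. SAP 14.2.4.1 tabulates death, respiratory failure, hospitalization and progression by arm, and 14.1.8 compares oxygen and ventilation use. A careful reader would see excess oxygen use beside the SpO2 curve. That stands, and it limits the harm. It does not correct the curve or its p-value, and a patient on home oxygen who stays in item 7 does not register as progression.

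It can also be said that room air is implied. That is weak: the same SAP list states room air for both respiratory rate and SpO2 in the composite and then omits it for this endpoint, so a programmer following the text would not apply it.

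Four stronger readings are tempting, and the documents do not support them:

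- That any patient put on oxygen is scored as recovered. The event needs a reading of 96% or more on oxygen, at a visit, in a patient not already at threshold, and it concerns this endpoint only.
- That the two SpO2 rules contradict each other. They belong to separately named endpoints and can both be applied; they are inconsistent and should be aligned.
- That the clinical-benefit objective cannot be answered. It has several other endpoints.
- That the bias has a known size. If 4–8 patients entered at 94–95%, one patient would be 1/8 = 12.5% to 1/4 = 25% of them. That is one patient's weight under an assumed count, not an expected effect.

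**Conclusion.** The point holds, within limits. Applied as written, the rule for this secondary endpoint can turn a worsening patient on oxygen into an early favourable event, and the planned best/worst-case comparison cannot reveal it. The clinical-signs composite is protected by its room-air condition, and the primary endpoint is safety.

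The size cannot be estimated. The documents give neither the number entering at 94–95% nor a rate of oxygen use, and entry requires a raised respiratory or heart rate rather than low SpO2, so few patients may be exposed. The 10-versus-7 responder contrast rests on every patient starting below 96% and three of ten in one arm going on oxygen; no p-value in either illustration falls below 0.05. In an unpowered proof-of-concept study of about 20 patients this should be corrected because the error reverses the meaning of the event and is cheap to remove, not because it is shown to change a conclusion.

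**What to change.** - In SAP Instructions (5), 14.2.1.4 and 14.3.8.7, define normal as SpO2 ≥ 96% in room air. Align the endpoint wording in protocol 1.1 and 3.
- State that a reading taken on supplemental oxygen or ventilation counts as not normalized.
- Identify such readings from the room-air status already needed for the clinical-signs endpoint, the oxygen and ventilation start and end dates behind table 14.1.8, and scale items 2–4. Item 7 alone will not do, because it merges limitation of activities with home oxygen.
- Flag readings whose oxygen status cannot be established and report how many there are. The SpO2 procedures do not ask for that status at each reading, and the documents do not show that the 14.1.8 dates capture all home oxygen.

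The cost is a wording change and a small amount of extra derivation. The downside is possibly fewer observed normalizations.

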**For CI and p-value (WI, within group):**

t denotes by using one sample t-test

w denotes wilcoxon sign rank test

(determined by Shapiro-Wilk normality test)

**For CI and p-value (between groups):**

Wilcox\_t denotes Wilcoxon rank-sum test (Mann-Whitney U Test) in t approximation

Wilcox\_z denotes Wilcoxon rank-sum test (Mann-Whitney U Test) in z approximation

ANOVA denotes Treatment effect in ANOVA model

ANCOVA denotes Treatment effect in ANCOVA model

For 95% CI (HL), HL denotes CI using Hodges-Lehman for median

## 14 TABLES AND FIGURES

- *The texts in shaded Italic are for programming note.*
- *Column of Study Site includes columns of {001-CARE, 002-CAR, Total}*
- *Column of Treatment Group includes columns of {CX-4945, SOC, Total}*
- *Column 'Difference' denotes pairwise comparison statistics.*
- *Multi-Selection means 'A subject may be counted in more than one category'*
- *Description in <...> will be presented according to data values.*
- *For column p-value: refer to Abbreviations of statistics in [Instructions and Abbreviations] above.*
- *For Groups Diff., §C = CX-4945, §S = SOC,*  
*T denotes two sample t test, W denotes Wilcox\_t (Wilcoxon rank-sum test in t approximation),*  
*C denotes Chi-Square test, F denotes Fisher's exact test*

## 14.1 DEMOGRAPHIC DATA AND BASELINE CHARACTERISTICS

### 14.1.1 Screen Failures and Subject Disposition by Study Site

Population: All Screened Subjects / Randomized Subjects

Characteristics	Study Site
. All Screened Subjects	
N	XXX
~Randomized Subjects	XXX (XXX.X%)
. Population of Randomized Subjects	
N	XXX
ITT	XXX (XXX.X%)
~ Safety	XXX (XXX.X%)
~ PP	XXX (XXX.X%)
~ Non-PP	XXX (XXX.X%)
~ <Reason 1>	XXX (XXX.X%)
~ <Reason 2>	XXX (XXX.X%)
...	XXX (XXX.X%)
. Treatment Arm of Randomized Subjects	
N	XXX
CX-4945	XXX (XXX.X%)
SOC	XXX (XXX.X%)
. Protocol Deviation of Randomized Subjects (Multi-Selection by Major/Minor & Category)	
N	XXX
~ Any Protocol Deviation	XXX (XXX.X%)
~ Major Protocol Deviation	XXX (XXX.X%)
~ <Reason 1>	XXX (XXX.X%)
~ <Reason 2>	XXX (XXX.X%)
...	
~ Minor Protocol Deviation	XXX (XXX.X%)
~ <Reason 1>	XXX (XXX.X%)
~ <Reason 2>	XXX (XXX.X%)
...	

### 14.1.2 Study Termination, Subject Disposition and Protocol Deviation

Population: Intention-to-Treat Population

Characteristics	Treatment Group
. Study Termination	
N	XXX
Study Completed	XXX (XXX.X%)
Study Not Completed	XXX (XXX.X%)
~ Withdrew consent	XXX (XXX.X%)
~ Protocol issue	XXX (XXX.X%)
...	XXX (XXX.X%)
. Study Duration [days]	TW
N (Missing)	XXX
Mean (SD)	XXX (XXX)
Median (IQR)	XXX (XXX)
Q1~Q3	XXX~XXX
Min~Max	XXX~XXX
. Population	
N	XXX
Safety	XXX (XXX.X%)
~ PP	XXX (XXX.X%)
~ Non-PP	XXX (XXX.X%)
~ <Reason 1>	XXX (XXX.X%)
~ <Reason 2>	XXX (XXX.X%)
...	XXX (XXX.X%)
. Protocol Deviation (Multi-Selection)	
N	XXX
~ Any Protocol Deviation	XXX (XXX.X%)
~ Major Protocol Deviation	XXX (XXX.X%)
~ <Reason 1>	XXX (XXX.X%)
~ <Reason 2>	XXX (XXX.X%)
...	XXX (XXX.X%)
~ Minor Protocol Deviation	XXX (XXX.X%)
~ <Reason 1>	XXX (XXX.X%)
~ <Reason 2>	XXX (XXX.X%)
...	XXX (XXX.X%)

Study Duration [days] = Date of Termination - Visit 1, or alternatively as the last visit date - Visit 1

### 14.1.3 Study Visits

Population: Intention-to-Treat Population

Characteristics	Treatment Group
. Repeat Variable:	
Study Visits Completed on ITT Population (Multi-Selection by Visit),	
Study Visits Completed on Safety Population (Multi-Selection by Visit)	
Study Visits Completed on PP Population (Multi-Selection by Visit),	
Adjusted Visits Completed on ITT Population (Multi-Selection by Visit),	
Adjusted Visits Completed on Safety Population (Multi-Selection by Visit)	
Adjusted Visits Completed on PP Population (Multi-Selection by Visit)	
N	XXX
Visit 1 (Screening)	XXX (XXX.X%)
Visit 2 (Day 1)	XXX (XXX.X%)
Visit 3 (Day 4)	XXX (XXX.X%)
~In-Person	XXX (XXX.X%)
~Remote (Phone/Telehealth)	XXX (XXX.X%)
Visit 4 (Day 8)	XXX (XXX.X%)
~In-Person	XXX (XXX.X%)
~Remote (Phone/Telehealth)	XXX (XXX.X%)
Visit 5 (Day 11)	XXX (XXX.X%)
~In-Person	XXX (XXX.X%)
~Remote (Phone/Telehealth)	XXX (XXX.X%)
Visit 6 (Day 14, EOT)	XXX (XXX.X%)
~In-Person	XXX (XXX.X%)
~Remote (Phone/Telehealth)	XXX (XXX.X%)
Visit 7 (Day 28, F1)	XXX (XXX.X%)
~In-Person	XXX (XXX.X%)
~Remote (Phone/Telehealth)	XXX (XXX.X%)
Visit 8 (Day 45, F2)	XXX (XXX.X%)
~In-Person	XXX (XXX.X%)
~Remote (Phone/Telehealth)	XXX (XXX.X%)
Visit 9 (Day 60, F3)	XXX (XXX.X%)
~In-Person	XXX (XXX.X%)
~Remote (Phone/Telehealth)	XXX (XXX.X%)

